Frailty is the primary outcome for this aim and is a new aim because it has not been measured prior to LA-E. It will be assessed using the Fried criteria [Fried, 2001] developed during the Cardiovascular Health Study. Frailty classification is based on the presence of five frailty characteristics: 1) walking speed standardized based on median height and sex, 2) grip strength standardized based on body mass index (BMI) and sex, 3) energy expenditure standardized based on sex, 4) exhaustion based on self-report, and 5) weight loss of 10 lbs or more in the last year without trying or intending to (based on self-report). Walking speed will be assessed using the timed short walk included in the Short Physical Performance Battery (SPPB) and grip strength. Energy expenditure will be based on kcal/week of energy derived from the Paffenbarger physical activity questionnaire. Exhaustion will be assessed using the question from the Geriatric Depression Scale, "Do you feel full of energy?." Weight loss will be assessed by self-report. (We acknowledge that this is a difficult item to interpret for the LA cohort, and will also examine the impact on a construct without this item.) Based on these assessments, frailty will be classified into three stages: non-frail (no frailty characteristics present), pre-frail (1 or 2 frailty characteristics present), and frail (3 or more frailty characteristics present). Our primary analysis will classify a person as having prevalent frailty if they are classified as frail during either of the LA-E visits. The proportion of participants experiencing any frailty will be compared between randomized groups using logistic regression, with clinic site, sex, and time from randomization to classification of frailty or the last non-frail classification as covariates. Odds ratios and 95% confidence intervals will be used to summarize the relative effect of the intervention on frailty.

Supporting analyses: include persistent major mobility disability (PMMD) based on repeated assessments of the adjudicated 400-m walk, sensitivity analyses for frailty and PMMD, falls, fractures, SPPB, grip strength, and Pepper Assessment Tool for Disability (PAT-D).

PMMD is considered present when an individual fails to complete two successive 400-m walks [Newman, 2006; Pahor, 2014]. Death after an initial MMD determination will also be considered

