Several **sensitivity analyses** will be performed for both frailty and PMMD: 1) covariates found to be predictive of missing outcomes will be entered into the logistic regression models to explore the effect of covariate dependent missingness on inference; 2) for the PMMD analysis, cases adjudicated as probable or possible MMD will be included as MMD cases to determine how robust the conclusions about the effect of the intervention on PMMD are to this broader classification of mobility disability, 3) for frailty, analyses will also be performed to compare the proportions not frail versus pre-frail or frail in each group, 4) multi-state survival models (PMMD) or transitional models for categorical outcomes will be used to compare the probability of transitions into and out of outcome states between participants randomized to the two intervention groups. Two absorbing states will be death and loss to follow-up. We will specifically evaluate the effect of the intervention on recovery from MMD or frailty. Recovery is defined as restoring the ability to complete a 400-m walk test after experiencing a MMD outcome or no longer being classified as frail. This evaluation will be accomplished by applying multi-state survival models to the disability and survival state data using the R msm and ELECT packages [van den Hout, 2013; Jackson, 2011] or using Proc Genmod of SAS™ to fit transitional models.

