Power: If 3800 participants are enrolled in LA-E and 8% in the DSE group will be classified as frail during LA-E, we project 80% power to detect an odds ratio of 0.70 (two-sided 0.05 type 1 error). Note that our preliminary data with a somewhat limited definition of frailty provide support for these assumptions: observed OR=0.75 [95% CI 0.57, 0.98] and 6.4% prevalence in the DSE group.

As noted earlier, LA-E plans to follow 3,800 participants through 2020, with collection of MMD data on two occasions, 2 years apart. If we assume 12.7% of the DSE group experience PMMD, a two-sided 0.05 probability of Type I error, and 1900 active participants in each group are followed for MMD, LA-E will have approximately 80% power to detect a 25% reduction in the

odds of PMMD in the ILI group compared to the DSE group. This percent relative reduction is consistent with what was observed in the LIFE [Pahor, 2014] trial (physical activity vs successful aging interventions) where the physical activity group had a 28% reduction in the hazard rate for PMMD.

5.4 Specific Aim 4 (secondary) is to test the hypothesis: the time until first occurrence of end stage renal disease (RRT or death from nephropathy) post-randomization will differ between intervention groups.

The primary outcome for diabetic nephropathy will be the first occurrence of **end stage renal disease (ESRD)**, defined as renal replacement therapy (RRT) or death from nephropathy. Information on outpatient and inpatient dialysis has been a crucial part of data collection since the beginning of the LA trial and has been collected every 6 months throughout. Renal transplants have been captured throughout follow-up, as well. This will continue in LA-E. The distribution of time to first occurrence of ESRD will be compared between ILI and DSE using survival analyses as described for total mortality (Section 5.1). Because data on ESRD will continue to be collected every six months in LA-E (as it was in LA and LA-C), censoring and follow-up times will cluster around these six month time points even though we will use the dates of the participant encounter to calculate follow-up time. Because 6-month intervals are fairly short and regular in length throughout follow-up, we will follow the commonly accepted recommendations [Leung, 1997] and will not complicate the analysis by considering interval censoring. All data since randomization will be used for analysis.

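### SAP 5.3 treats recovery from frailty or mobility disability as an intervention effect, but only people selected after randomization can recover

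*Combined protocol and SAP*

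**What the plan says.** The main analyses in SAP 5.3 are arm comparisons that do not condition on becoming frail or disabled. A person counts as frail if "classified as frail during either of the LA-E visits", and the proportions with any frailty and with any persistent major mobility disability (PMMD) are compared by logistic regression.

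The fourth sensitivity analysis goes further. Multi-state or transitional models will "compare the probability of transitions into and out of outcome states between participants randomized to the two intervention groups". On the end states the SAP says: "Two absorbing states will be death and loss to follow-up". It then commits to a specific claim: "We will specifically evaluate the effect of the intervention on recovery from MMD or frailty". The definition follows: "Recovery is defined as restoring the ability to complete a 400-m walk test after experiencing a MMD outcome or no longer being classified as frail".

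Two other statements in 5.3 bear on this. Frailty is described as "a new aim because it has not been measured prior to LA-E", so no baseline frailty status exists. The power paragraph assumes that "8% in the DSE group will be classified as frail during LA-E, we project 80% power to detect an odds ratio of 0.70", and it also assumes 25% lower odds of PMMD under ILI.

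For the recovery comparison the SAP gives no severity adjustment, no principal-stratum or other causal estimand, no caveat, no expected numbers and no power. SAP 5.6 does discuss confounding of post-randomization factors and cites principal stratification, but only for the mediation analyses.

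**The concern.** A person can recover only after entering the affected state. Entry happens after randomization, and the trial's own hypothesis is that ILI changes who enters. If ILI mainly prevents mild, reversible cases, the ILI cases that remain are harder to reverse than the DSE cases, and ILI appears to impair recovery. If it mainly prevents severe cases, ILI appears to help. In both situations the recovery contrast reflects who became frail or disabled, not what ILI does to them afterwards. A multi-state or transitional model estimates the same conditional transition and does not restore the balance that randomization gave.

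At stake is a published statement that ten years of lifestyle intervention helps or hinders recovery from frailty or mobility disability when it may do neither.

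**Working it through.** **1. The plan's own figures.** Inputs from the SAP 5.3 power paragraphs: 3800 participants (taken as 1900 per arm); frailty 8% in DSE with OR 0.70; PMMD 12.7% in DSE with OR 0.75; two-sided 0.05. The ILI rate is p·OR/(1 − p + p·OR).

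- Frailty: 0.056/0.976 = 5.74%. Expected cases: 152 DSE and 109 ILI. The two-proportion power is 78.7%, against 80% stated.
- PMMD: 0.09525/0.96825 = 9.84%. Expected cases: 241 DSE and 187 ILI. Power is 79.7%, against about 80% stated.

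The stated power is reproduced to within 2 points. So under the SAP's assumptions ILI removes about 152 − 109 = 43 frailty cases from the group that could recover.

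**2. Recovery contrast when the true effect is zero.** Assumptions not in the documents: half of DSE cases are mild and half severe (76 each); recovery is 50% if mild and 10% if severe, identical in both arms. DSE recovery is then 30.0%.

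If all 43 avoided cases are mild, ILI keeps 33 mild and 76 severe cases. ILI recovery = (33 × 0.5 + 76 × 0.1)/109 = 24.1/109 = 22.1%. The OR is (0.221/0.779)/(0.300/0.700) = 0.66. With pooled SE 0.0555, unpooled SE 0.0544 and difference 0.079, the rejection probability is Φ[(0.079 − 1.96 × 0.0555)/0.0544], or about 29%.

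| Cases ILI avoids | DSE recovery | ILI recovery | Spurious OR | False-positive rate |
|---|---|---|---|---|
| all mild | 30.0% | 22.1% | 0.66 | about 29% |
| 75% mild | 30.0% | 26.1% | 0.82 | about 11% |
| proportional | 30.0% | 30.0% | 1.00 | 5% |
| 75% severe | 30.0% | 33.9% | 1.20 | about 10% |
| all severe | 30.0% | 37.9% | 1.42 | about 27% |

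- With recovery of 40% and 20% instead, the OR runs from 0.82 to 1.20 and the false-positive rate reaches about 11%.
- With recovery unrelated to severity, the OR is 1.00 in every row.
- With severity continuous and a uniform log-odds prevention effect, the OR is 0.89 to 0.97 and the rate 5% to 7.5%. With prevention varying by severity, the OR is 0.65 to 1.41 and the rate 8% to 29%.
- With the PMMD counts and 50%/10% recovery, the OR runs from 0.74 to 1.30 and the rate reaches about 27%. PMMD is only a proxy here, because the rate of a first MMD is not stated.

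The counts of 152 and 109 are upper bounds: the 8% is for either visit, and recovery can be seen only in people frail at exam 1. Fewer cases leave the ORs unchanged and lower the false-positive rates.

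**3. Precision for frailty.** Assumptions: 5%–6% of DSE frail at exam 1, OR 0.70, 85% reassessed at exam 2, 40% recovery in DSE.

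- 5%: ILI 0.035/0.985 = 3.55%. Cases 95 and 68; reassessed 81 and 57.
- 6%: ILI 0.042/0.982 = 4.28%. Cases 114 and 81; reassessed 97 and 69.

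The smallest ILI recovery detectable with 80% power is 64% and 62% respectively. SAP 4.3 implies better return before deaths (0.98² × 0.95 = 91%), which gives 63% and 61%. Using the 8% upper bound with 85% return gives 59%.

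**The case against.** The strongest reply is that little depends on this analysis. It is the fourth sensitivity analysis under a secondary aim, and the main frailty and PMMD comparisons do not condition on the affected state. Recovery would be reported beside onset, since transitions in both directions are modelled. SAP 5.1 already plans an arm comparison of expected disability-free survival with the same software, and it admits that such models are hard to read as a summary of an intervention's effect. The larger biases above also need prevention to be concentrated in one part of the severity range, and no figure in the documents supports that.

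Most of this stands, and it limits the scope and size of the point. It does not answer it. The caution in SAP 5.1 is not attached to the recovery analysis. The planned disability-free survival rests on the PAT-D index and does not cover frailty. Two exams cannot readily show which severity pattern holds, yet the SAP still commits to calling the result an intervention effect.

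Two stronger readings are tempting. A reader might infer that the analysis will show ILI impairing recovery by a sizeable margin. A latent-vulnerability model can give 75% versus 67%, or 48% versus 37%, but only if ILI prevents exam 1 frailty solely in less vulnerable people and nothing differs between arms at exam 2. A uniform prevention effect gives gaps of only about 1 to 8 points, and preventing severe cases reverses the sign. A reader might also infer that mobility recovery is equally imprecise. The documents do not support that: MMD has three clinic walks, six-monthly telephone information and a repeat walk for first failures at the last visit, and no MMD rate is given.

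**Conclusion.** The recovery comparison in SAP 5.3 is not protected by randomization, and as written it can yield an apparent effect of ILI on recovery where none exists. That follows from the SAP's own definition of recovery and its own Aim 3 hypothesis.

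The size and sign of the bias cannot be fixed from the documents. For frailty, under the assumed recovery rates and severity mix, the spurious OR runs from about 0.65 to 1.4 and the false-positive rate from 5% to about 29%. Both extremes are unfavourable scenarios. The bias is zero if prevention leaves the severity mix unchanged or recovery is unrelated to severity. Separately, frailty recovery is imprecise: about 40% versus 62%–64% is the smallest contrast detectable with 80% power, given 5%–6% frail at exam 1 and 85% return.

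It would go too far to conclude that the whole multi-state analysis is unsound or that Aim 3 is compromised. The same models can support whole-arm summaries, and the main frailty and PMMD comparisons and both primary aims are unaffected. The defect is the causal label on one transition.

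**What to change.** In sensitivity analysis 4 of SAP 5.3:

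- Base any statement of an intervention effect on state occupancy at exam 2, compared by original assignment among all LA-E participants. The states are alive and non-frail (or able to complete 400 m); frail or disabled; dead; lost to follow-up.
- Compute occupancy from the transition model combined with each arm's exam 1 state distribution. The transition probabilities alone are conditional on the starting state and are not enough.
- For mobility, link this to the disability-free survival analysis in SAP 5.1.
- Keep the recovery transition estimates, labelled descriptive and non-randomized, with no claim of an intervention effect.

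Frailty can be compared only in LA-E enrollees (3800 expected of 5145 randomized), a limit that the main frailty analysis shares. No new data are needed. The cost is a change of wording and a small amount of added analysis. Occupancy answers a different question from recovery, so recovery would no longer be reported as a causal effect.

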When repeated outcomes are available, continuous outcomes will be analyzed using linear mixed effects models to estimate the intervention effects. Count data (e.g., number of hospitalizations) will be analyzed using Poisson or negative-binomial regression, for which the natural log of the follow-up time will be included in models as an offset term. Generalized linear models, including generalized estimating equations (GEE) for repeated measures, will be used to analyze binary outcomes with a logit link function.

For each specific aim, we clearly identify the timeframe for analyses.

- For some outcomes (e.g. mortality, renal replacement therapy) inference involves data collected through the full span of LA, LA-C, and LA-E follow-up. It is necessary to have the full span of follow-up to have adequate power for these outcomes. We will, in supporting analyses, estimate intervention effects during the intervention phase and post-intervention phases of follow-up, but the primary comparisons will span these two time periods.

- Other outcomes (e.g. costs, SF-36) have been featured in publications from the intervention phase of the trial (prior to 9/2012 in LA). For these, LA-E aims and principal inferences are based on data collected post-intervention and we project to have sufficient power for these comparisons. In supporting analyses, we will also portray data by intervention assignment from the time of randomization, but this will be for descriptive purposes.
- Some outcomes (e.g. frailty) have not been measured previously in LA , so that inference is based solely on LA-E data.

In projecting statistical power, we have made the following assumptions. For mortality, we have assumed that the percentage of individuals who we are unable to track with respect to mortality would accrue at 1%/yr. We have also assumed that the inability to establish mortality status on participants who were actively followed will also additionally accrue at 1%/yr. For general data collection, we assume that lost follow-up will accrue at 2%/yr (note that throughout the first 12 years of LA, lost follow-up accrued at 1.2%/yr). We also project that we will continue to obtain clinic-based measures on >95% of participants who are currently active (i.e. who are not lost to follow-up for general data collection).

4.4 Missing data.

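### The 80% power stated for frailty holds approximately only if all 3,800 enrollees are classified, and the preliminary data cited in its support are less favourable than the planning values

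*Combined protocol and SAP*

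**What the plan says.** The Power paragraph of SAP section 5.3 sets its condition as "If 3800 participants are enrolled in LA-E and 8% in the DSE group will be classified as frail" and concludes "we project 80% power to detect an odds ratio of 0.70 (two-sided 0.05 type 1 error". It mentions no evaluable number below 3,800. It then adds that "our preliminary data with a somewhat limited definition of frailty provide support for these assumptions", and gives those data as "observed OR=0.75 [95% CI 0.57, 0.98] and 6.4% prevalence in the DSE group".

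SAP section 4.3 lists the assumptions behind the power projections. For general data collection, "we assume that lost follow-up will accrue at 2%/yr". The study also expects to "obtain clinic-based measures on >95% of participants who are currently active".

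SAP section 5.3 and protocol section 1.4.2 build frailty from five Fried characteristics, which include a timed walk and grip strength measured at the clinic exams. The primary frailty analysis counts a person as frail if frail at either of the two LA-E visits. It compares the arms by logistic regression.

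**The concern.** Two things do not fit together.

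- Section 4.3 sets out loss and completeness assumptions for power, and frailty depends on attending an exam. The frailty statement nevertheless treats every enrollee as classified. The mortality and cost power paragraphs (sections 5.1 and 5.2) say that they use the section 4.3 assumptions; this one does not.
- The preliminary data are offered as backing for OR 0.70 and 8%, yet both estimates lie on the unfavourable side: a weaker effect and a lower prevalence.

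Frailty is the first secondary aim. A reader told that power is 80%, with the study's own data behind it, would give a null result more weight than the design earns if the true effect is near the preliminary one.

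**Working it through.** **Inputs.** Section 5.3: 3,800 enrolled, DSE prevalence 8%, OR 0.70, two-sided 0.05; preliminary OR 0.75 (CI 0.57 to 0.98) and 6.4%. Protocol section 1.3.7: 1:1 randomization, so 1,900 per arm. Section 4.3: 2% per year lost; clinic measures on more than 95% of active participants.

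**Formula.** Two proportions, pooled variance under the null, no continuity correction:

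power = Φ{ [Δ − 1.96·√(2p̄(1−p̄)/n)] / √([p₁(1−p₁)+p₂(1−p₂)]/n) }

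Here p₁ is the DSE prevalence, p₂ the ILI prevalence implied by the OR, Δ = p₁ − p₂, and p̄ their mean.

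**Step 1: the plan's own figure.** The DSE odds are 0.08/0.92 = 0.0870. Times 0.70 gives 0.0609, so p₂ = 0.0609/1.0609 = 0.0574. Then Δ = 0.0226 and p̄ = 0.0687. At n = 1,900 the standard errors are 0.00821 (null) and 0.00820 (alternative). The standardised value is about 0.80 and power is 78.7%. The OR that gives exactly 80% is 0.696, which rounds to the stated 0.70. The stated figure therefore follows from its inputs with no loss. Exactly 80% at OR 0.70 would need 1,961 per arm, so there is no reserve to absorb loss.

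**Step 2: loss (assumed).** The SAP does not say how section 4.3 applies to frailty. Because of the either-visit rule, one exam is enough to contribute. Two cases are taken:

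- 5% never examined: 3,800 × 0.95 / 2 = 1,805 per arm.
- A further 2% (one year at the SAP's rate) lost before any exam: 3,800 × 0.95 × 0.98 / 2 ≈ 1,769 per arm.

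**Step 3: the preliminary values.** OR 0.75 gives p₂ = 6.12% from 8%, and 4.88% from 6.4%.

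| Classified per arm | OR 0.70, 8% | OR 0.75, 8% | OR 0.75, 6.4% | OR for 80% power at 8% |
|---|---|---|---|---|
| 1,900 (no loss) | 78.7% | 61.8% | 52.9% | 0.696 |
| 1,805 | 76.7% | 59.6% | 50.9% | 0.689 |
| 1,769 | 75.8% | 58.7% | 50.1% | 0.686 |

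Loss costs 2 to 3 points. With no loss, moving the OR from 0.70 to 0.75 costs 78.7 − 61.8 ≈ 17 points, and moving prevalence from 8% to 6.4% costs a further 61.8 − 52.9 ≈ 9.

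**Step 4: how far the preliminary data conflict with OR 0.70.** The interval gives SE(log OR) = ln(0.98/0.57)/3.92 = 0.138. The distance from 0.75 to 0.70 is ln(0.75/0.70) = 0.069, or 0.5 SE. The data are compatible with 0.70. The interval also reaches 0.98, so they do not single it out.

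**The case against.** The case for leaving the text alone has weight.

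- **Calculation.** A reader might infer a slip in the 80%. The documents do not support that: the detectable OR is 0.696, and the paragraph is openly conditional on 3,800.
- **Size of the loss.** The 95% is a floor, one exam suffices, and home and nursing-home visits are planned (protocol section 1.3.5). Section 4.3 also refers to participants currently active, and 3,800 is already 96% of those (protocol section 1.3.3). On that reading about 3,800/0.96 × 0.95 ≈ 3,760 would be measured, or 1,880 per arm, with 78.3% power. In the other direction, a reader might apply 9% loss over 4.5 years plus 5% unmeasured (1,643 per arm, 72.7%). The either-visit rule does not support that, since loss after a first exam does not remove the participant.
- **Preliminary data.** They used a narrower definition at 6.4%, and counting frailty at either of two visits could raise prevalence. This stands, but the planned 8% is the SAP's own figure, and OR 0.75 at 8% still gives only 62% before loss. Reaching 80% at OR 0.75 with 1,900 per arm would take about 12.9% prevalence, which the SAP nowhere projects. A reader might also take 53% to 62% as what the preliminary data imply. Only 53% rests on them alone; 62% pairs their OR with the planning prevalence.
- **PMMD.** A reader might extend the discount to PMMD. Section 5.3 uses six-monthly telephone reports when the 400-m walk is missing and counts death after a first failure. The PMMD statement claims only approximately 80% with 1,900 per group followed, and it reproduces at 79.7%.
- **Consequence.** The cohort is fixed, the aim is secondary, and results come as odds ratios with intervals. This limits the harm but does not make the power statement accurate.

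**Conclusion.** The concern holds as a matter of planning inputs and wording. The stated 80% requires every enrollee to be classified. With 1,769 to 1,805 per arm classified, power is about 76% to 77% for OR 0.70 at 8%, and the OR detectable with 80% power is about 0.69. That part is modest and depends on the assumed loss.

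The larger gap needs no assumption about loss. The preliminary OR and prevalence together give about 53% power with all 3,800 classified, and 50% to 51% after the assumed loss. With the planned 8%, OR 0.75 gives 62%, or 59% to 60% after loss. Those data are compatible with the planning OR but do not support 80% power.

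**What to change.** In the Power paragraph of SAP section 5.3, state the number per arm expected to have at least one classifiable exam and how it follows from section 4.3. Then restate the power along these lines:

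> Assuming 1,769 to 1,805 participants per arm are classified at one or more exams, power is about 76%-77% for an odds ratio of 0.70 with 8% frailty in DSE (80% for an odds ratio of about 0.69). At an odds ratio of 0.75, power is about 50%-60% for DSE prevalence of 6.4%-8%.

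Replace the clause that presents the preliminary data as support with a statement that those estimates come from a more limited definition, are compatible with OR 0.70 (CI 0.57 to 0.98), and are less favourable than assumed. If the investigators expect the full definition and the either-visit rule to raise prevalence, they should say so and by how much. Leave the PMMD power statement unchanged.

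The cost is SAP wording only. Design, data collection and analysis do not change; the stated power becomes less favourable.
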